4.2 Objectives

- 4.2.1. The objectives for the feasibility study are to:
- Develop a specialist antenatal clinical service for the management of pregnancy subsequent to stillbirth for women

- Assess the acceptability, implementation and uptake of the proposed antenatal clinical service. Components of which include: (i) specialised antenatal clinical care and (ii) psychosocial support and preparation for birth.
- Explore impacts of the research on practice / services and delivery of the intervention
- Assess recruitment, retention, compliance of women in the study
- 4.2.2. To prepare for a full-scale evaluation, we will also:
- Define the most appropriate research design for a full-scale evaluation trial
- Choose the most appropriate primary and secondary outcomes to assess the effect of the intervention in a full-scale trial
- Assess the acceptability and burden associated with data collection for participants.
- Use data to assess the sample size required for a full-scale trial
- Determine the feasibility of an economic evaluation, through an exploration of key resources associated with implementing the intervention and how these may be reliably captured.
- 4.2.3. To synthesise all feasibility, acceptability and uptake data, to develop a full trial protocol at the end of the study.

5) STUDY DESIGN & PROTOCOL

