- Women booking at the study site will be recruited during months 4 and 5 to explore experiences of attending the specialised antenatal clinic, worries in pregnancy and preparation for pregnancy and asked to complete questionnaires, at the beginning and towards the end of their pregnancy. A sub-sample of women will also be invited to attend focus group interviews or individual interviews, whichever they prefer, towards the end of their pregnancy to capture pregnancy experiences, including impacts of the intervention (study months 4-12).
- Monthly meetings (attended by the specialist antenatal clinical care staff, research team facilitator, hospital staff including managers and administrators) to share experiences and develop further strategies to improve clinical care practice and outcomes for women will be planned (study months 4-12).
- Health workers (midwives, nurses, obstetricians, and support staff), and other
 hospital staff, including managers and administrators, directly involved in the
 intervention will be asked to compete a staff experience questionnaire and offered
 the opportunity to attend a focus group interviews at the end of Phase 2 (study
 month 12).

6) STUDY PARTICIPANTS

6.1 Inclusion Criteria:

Pregnant women booking at the study site for antenatal care (during Phases 1 and
 with subsequent pregnancy following stillbirth (baby born dead at 28 weeks

gestation or more, with a birth weight of 1000grams or more or a body length of 35cm or more (WHO, 2019))

OR

Health workers (midwives, nurses, obstetricians, and support staff), and other hospital staff, including managers and administrators directly involved in the study intervention or who provide care of services to pregnant women at the study site.

• 18 years or over, at the time of recruitment (women).

6.2 Exclusion Criteria:

• Unable to give consent (women)

6.3 Recruitment:

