Staff and others directly involved in the delivery of the intervention will be informed about the research during workshops facilitated by the research team at the beginning of the study. They will be invited to contact the research team directly if they are interested in participating and given a written and verbal explanation. Potential participants will be reassured that they are under no obligation to participate and can withdraw at any time up to 1 week after the focus group interview. They will be asked for permission to re-contact by their preferred method, once they have had time to consider participation and not less than 24 hours later. If the health worker or other agrees to participate, they will be provided with the planned date of the focus group interview (Phase 1 & 2). On the agreed focus group date, the research assistant/midwife will bring the study information and consent form, and will take approximately 10 minutes to discuss the study and read through the consent form with the potential participants in order to ensure that the content is well understood. A further opportunity will be provided for questions to be asked of the researchers. If the potential participant agrees to take part, they will be asked to sign the consent form.

In addition, at the end of phase 2, the health workers in the facility will be invited in writing to complete a short, anonymous paper questionnaire to assess awareness of the research, experiences of either routine antenatal care or the intervention and to capture any wider impacts on practice. The questionnaire will be accompanied by participant information, return will be taken as confirmation of consent.

6.4 Participants who withdraw consent:

At the point of recruitment, all participants will be informed that participation in the research is voluntary and that they can withdraw consent at any time up to the point of 1 week after the focus group discussion / individual interview without giving any reason, without their current or future care or legal rights being affected. Data collected up to the time participant leaves the study or is lost to follow up will continue to be included in the findings. Participants will be informed that no data can be removed once the findings are anonymised and sent for publication.

7) OUTCOME MEASURES

The key feasibility outcomes will be recruitment and retention of women in the study.

Other outcomes will include:

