8.5. Health economics

Data will be captured to identify the key resources associated with the intervention, including:

Human resources (direct) – the intervention log as described above will be used to identify person (antenatal clinical care staff) time spent performing all aspects of the intervention, including attending training and meetings.

Indirect resources – as part of the staff experience questionnaire, clinic staff will be asked about their perceived impact of the intervention on human and other resources and any additional equipment purchased in order to deliver the intervention.

Antenatal visits and out of pocket expenses – women will be asked in the questionnaire survey to report all antenatal visits and any interventions (e.g. scans) and about any out of pocket expenses incurred related to the intervention e.g. travel costs for attending additional specialist antenatal classes.

9) DATA ANALYSIS AND STATISTICAL CONSIDERATIONS

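### The only source named for additional equipment is an end-of-study staff questionnaire, apparently anonymous, so quantities, dates and prices cannot be verified or de-duplicated

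*Protocol*

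**What the plan says.** Objective 4.2.2 of the protocol is to judge whether an economic evaluation is feasible "through an exploration of key resources associated with implementing the intervention and how these may be reliably captured". Section 8.5 opens with the matching purpose: "Data will be captured to identify the key resources associated with the intervention". It then assigns a source to each kind of resource. Staff time comes from the intervention log. Antenatal visits and out-of-pocket costs come from the women's survey. For indirect resources, the staff experience questionnaire is used, and in it "clinic staff will be asked about their perceived impact of the intervention on human and other resources and any additional equipment purchased".

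Section 6.3.2 describes a staff questionnaire at the end of Phase 2: "the health workers in the facility will be invited in writing", and the form is short, on paper and anonymous, with its return taken as consent. Section 5.4.2 describes the month 12 questionnaire as going to staff directly involved in the intervention, managers and administrators included, who "will be asked to compete a staff experience questionnaire and offered" a focus group. Sections 8.2 and 8.3 also place the staff experience questionnaire at the end of Phase 2.

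**The concern.** A purchase is a discrete event that normally leaves a record. Section 8.5 relies instead on what a group of staff remember at the end of the study, apparently on forms that cannot be traced to a respondent. One item may be named by several people or by nobody, and a vague answer cannot be followed up.

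At stake is one part of the economic feasibility work. Reliable capture of resources is itself something the study sets out to learn. With a single source that cannot be checked, the team could finish the study without knowing whether asking staff is an adequate way to record equipment in the full-scale trial. An analysis plan could not repair this afterwards, because the limitation lies in how the data are collected.

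**Working it through.** The protocol states no equipment count, cost or formula, so there is no figure to reproduce. The check sets the relevant sections side by side.

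**1. Is there another named source for equipment?**
- Intervention log (8.3.1): training, meetings, administration, contacts with women, time spent and mode of support. Equipment is not listed.
- Use of the log in 8.5: staff time only.
- Case report forms (section 7): data on the women and their pregnancies.
- Women's survey (8.5): visits, interventions received and out-of-pocket costs.
- Purchasing, invoice or asset records: not mentioned anywhere.

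The staff questionnaire is therefore the only source named.

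**2. Is that questionnaire anonymous?** Section 8.5 does not say so; anonymity is stated in 6.3.2. Both sections describe a questionnaire to staff, and 5.4.2, 6.3.2, 8.2 and 8.3 all place one at the end of Phase 2. That they are the same form is a strong inference, not an explicit statement.

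**3. How long is the recall period?** The clinic launches in month 4 and the questionnaire is given in month 12 (both 5.4.2): 12 − 4 = 8 months. For anything bought before launch it is longer.

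**4. How many people might report one purchase?** With k returned forms, one purchase can be mentioned 0 to k times. The protocol does not fix k:
- Specialist team only (5.4.1: one obstetrician, two midwives, one support worker): k = 1 + 2 + 1 = 4, so 0 to 4 mentions.
- All staff up to the recruitment maximum (5.3): k = 30, so 0 to 30 mentions.
- Health workers across the facility (6.3.2): no number is given.

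These are arithmetic limits under assumed numbers of respondents, not estimates of likely error.

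**5. What can be recovered from the forms?** Suppose m forms each report one unit of the same item.
- Item type: recoverable, since m mentions collapse to one entry on a list.
- Quantity: anything from 1 unit (all m describe the same purchase) to m units (each describes a different one) fits the forms. With m = 3, the answer could be 1, 2 or 3.
- Date and price: conflicting or missing answers cannot be resolved, because an anonymous respondent cannot be contacted.

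**The case against.** The strongest reply is that the protocol promises no more than this source can deliver. It speaks of identifying and exploring key resources, and the resource outcome in section 7 has no unit, cost or total. For a list of the kinds of equipment one clinic needed, duplicate mentions do no harm and anonymity is no obstacle. This stands. A reader might infer that equipment is to be counted and that the resulting total would be biased or impossible to form. The documents do not support that: no count or total is planned, item types remain identifiable, and a later check with managers is not ruled out.

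It would also be unfair to call the source a mere opinion survey. In 8.5, perception qualifies the impact on resources; what was purchased is a factual question. Nor are all respondents remote from purchasing, because 5.4.2 includes managers and administrators directly involved in the intervention. Monthly meetings and a month 12 focus group give further occasions to raise equipment, although the protocol assigns it to neither.

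Finally, trying out a questionnaire is a legitimate way to learn how to capture a resource, and a poor result would be informative. This stands only in part. A poor result can be recognised only against something else, and no comparator is named.

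**Conclusion.** The point holds in a limited form. The one source named for additional equipment can support a list of item types, but not verified or de-duplicated quantities, dates or prices, and the study has no planned means of showing whether this way of capturing equipment is reliable. That falls short of the reliability part of objective 4.2.2.

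The conclusion rests on two readings: that the staff experience questionnaire of 8.5 is the anonymous form of 6.3.2, and that more than one person answers it. If the form were not anonymous, answers could be followed up, but equipment would still rest on one recall-based source. No numerical size can be put on the effect, since the protocol sets no equipment figure and no number of respondents.

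The matter is minor. It touches neither key feasibility outcome (recruitment and retention, section 7) nor the progression criteria in 9.1.1.

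**What to change.** In 8.3.1, add an equipment line to the intervention log: item, number, date, and price where available, entered once per purchase from hospital or study purchasing records where these exist. In 8.5, name the log as the main source for additional equipment, and keep the staff questionnaire for perceived impact and as a cross-check. Comparing the two would then give direct evidence on how well staff report captures equipment.

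The cost is a short wording change in two sections, one more line in a log already being kept, and a small recording task for whoever makes the entries. It depends on access to purchasing records, which the protocol does not describe. Where no record can be obtained, the entry can be made at the time of purchase with the price left blank.

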Individual consent will not be sought for attendance at either the current antenatal clinic (control phase 1) or the proposed specialised antenatal clinic (intervention phase 2), as both are considered standard practice. The current antenatal clinic running throughout Phase 1 will be superseded with the specialised antenatal clinic in Phase 2 of the study period. Both will be provided for all women attending antenatal services at the study site who have experienced a previous stillbirth, irrespective of their participation in the study / questionnaire completion / focus group / individual interview participation.

Consent will be sought for data collection associated with the assessment of the feasibility of a full-scale trial, acceptability and uptake of the intervention for women and facility staff. Identification of women with a history of stillbirth will be undertaken by appropriately trained and experienced members of the clinical team and confirmation of eligibility and consenting of participants undertaken by research assistants/midwives.

6.3.1. Women:

Eligible women will be initially identified and approached via a member of the clinical care team at the woman's hospital booking appointment who will introduce the study. If

permission to consider the study has been granted, they will notify the research assistant/midwife to discuss the study further. Written and verbal information (available in local languages) will be supplied and potential participants will be given time to consider participation. The woman will be encouraged to discuss with family/others (if accompanying her) and provided additional opportunities to ask questions. She will be informed that her participation is voluntary and a decision not to take part in the research will have no impact on her current or future healthcare provision. Women will be given the opportunity to confirm participation at the booking visit should they wish and provided with the consent form to sign. Others will be given the opportunity to confirm participation at their next antenatal clinic appointment, where consent form completion will take place. Women will be able to withdraw up until 1 week after taking part in the interviews.

6.3.2. Health workers (midwives, nurses, obstetricians, and support staff) and other hospital staff, including managers and administrators:

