- Acceptability and uptake of the intervention and experiences of study processes
 which will be explored through questionnaires and interviews with women (Flenady
 et al 2016, Wojcieszek et al 2016) and healthcare staff (midwives, nurses,
 obstetricians, and support staff), involved with the delivery of antenatal care.
- Psychological measures:
 - Cambridge Worry Scale (Green et al 2003), a 16-item content-based measure specifically designed to assess the extent and content of worries in pregnancy (women).

- Birth Preparedness and Complications Readiness Tool (JHPIEGO 2004), a atructured questionnaire to assess knowledge, attitudes and perceptions of preparation for childbirth (women).
- Questionnaire to assess awareness of the research, experiences of either routine antenatal care or the intervention and to capture any wider impacts on practice (women & staff).

Clinical measures:

- o Investigator-designed case report forms will be used to collect data for women participants via patient health records (including hospital, patientheld and electronic records) and self-report (where no secondary source available): Demographic (age, ethnicity, socioeconomic status [highest level of education, occupation]) medical (history, body mass index, smoking status, medication use), obstetric history (previous pregnancies, mode of birth, outcomes), current pregnancy and outcome. Previous stillbirth data including the onset of labour, mode of birth, maternal and infant outcomes, cause of death (if known) length of hospital stay, and postnatal complications/all healthcare utilisation (for example; antenatal visits to the hospital, ultrasound scans) and access to external support will be collected. Data will be collected at recruitment and birth (study completion).
- Basic demographic data (age, job title, year qualified, area of work) will also be collected via self-report for participating health workers and support staff at recruitment (staff).
- Human and healthcare resources associated with delivering the intervention.

8) DATA COLLECTION, SOURCE DATA AND CONFIDENTIALITY

8.1. Recruitment and retention:

A participant log of women who are eligible but not invited to participate, invited to participate in the study, those recruited and any participants who leave the study before completion will be kept. Reasons for non-recruitment (e.g. refusal to participate, language

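### Out-of-pocket expenses are asked only in relation to the intervention, so costs to women are not piloted in the usual-care cohort and have no comparator

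*Protocol*

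**What the plan says.** Section 8.5 of the protocol opens with "Data will be captured to identify the key resources associated with the intervention, including" and lists three sources: staff time from the intervention log, staff views on indirect resources, and reports from the women. The women's reports have two parts with different scopes. On use of care, "women will be asked in the questionnaire survey to report all antenatal visits and any interventions (e.g. scans", with no restriction to one phase. On spending, they are asked about "any out of pocket expenses incurred related to the intervention e.g. travel costs for attending additional specialist antenatal classes".

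The objective behind this, in Section 4.2.2, is to "Determine the feasibility of an economic evaluation, through an exploration of key resources associated with implementing the intervention and how these may be reliably captured". Section 7 lists as an outcome "Human and healthcare resources associated with delivering the intervention". The case report form in Section 7 also records use of care, such as visits and scans, but mentions no costs.

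Section 5.4.1 gives Phase 1 women existing care. It also makes Phase 1 the place to learn what usual care consists of and to try out the data collection tools for the later trial. Section 6.3 states how the two services relate: "The current antenatal clinic running throughout Phase 1 will be superseded with the specialised antenatal clinic in Phase 2".

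**The concern.** The specialised clinic replaces the current one. Part of what a Phase 2 woman spends on travel or scans therefore takes the place of what a Phase 1 woman spends on the same things. The cost of the new service to women is a difference between two totals, and Section 8.5 asks about one side only.

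This is a matter of data collection. An expense that was never asked about cannot be recovered by a later analysis plan. What is at stake is the feasibility question itself: whether women's costs can be captured well enough to support an economic evaluation. Such an evaluation compares two forms of care, and Section 5.1 expects the full trial to be a stepped wedge, in which clusters would be observed under usual care before they cross over. A cost question that can be answered only under the intervention would enter that trial untested in the control condition.

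**Working it through.** **Step 1. What each cohort can report.**

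| Item | Phase 1 | Phase 2 | Source |
|---|---|---|---|
| Visits and scans | Asked | Asked | Sections 7, 8.5 |
| Expenses tied to the intervention | None can arise under existing care | Asked | Sections 5.4.1, 8.5 |
| Expenses of routine antenatal care | Not asked | Depends on how the item is read | Section 8.5 |

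No other section of the protocol collects women's expenses.

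**Step 2. How many women this affects.** Section 5.3 expects 25 to 30 eligible women per two-month recruitment period and 25% refusal.

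- Per phase: 25 × 0.75 = 18.75 and 30 × 0.75 = 22.5, which agrees with the protocol's figure of about 20.
- Both phases: 2 × 18.75 = 37.5 and 2 × 22.5 = 45.
- Share with no expense data: 18.75 / 37.5 = 22.5 / 45 = 50%.

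**Step 3. Whether a planned estimate is affected.** Section 9.1.3 plans confidence intervals for differences between cohorts, and variances, under a heading that covers psychological assessments and clinical data. Sections 4.2.2, 7 and 8.5 name no cost difference. No planned estimate depends on the expense item.

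**Step 4. Which way a cost difference would err if someone formed one anyway.** Suppose control spending were set to zero, which the protocol does not instruct. Assume a cost of 1 unit per attendance, v1 usual-care visits, v2 specialised-clinic visits and k additional classes. The protocol gives none of these values.

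- True difference = v2 + k − v1.
- Reading A counts every attendance at the specialised clinic. It records v2 + k, so the error is +v1.
- Reading B counts only the additional classes, which is the protocol's own example. It records k, so the error is v1 − v2.

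| v1 | v2 | k | True | A records (error) | B records (error) |
|---|---|---|---|---|---|
| 4 | 4 | 3 | 3 | 7 (+4) | 3 (0) |
| 4 | 6 | 3 | 5 | 9 (+4) | 3 (−2) |
| 4 | 8 | 3 | 7 | 11 (+4) | 3 (−4) |
| 6 | 4 | 3 | 1 | 7 (+6) | 3 (+2) |

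The error is always upward under A. Under B it can be zero, downward or upward. The sign turns on a reading and on visit counts that the protocol does not fix.

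**The case against.** **The objective covers intervention resources only.** Section 4.2.2 speaks of the resources needed to implement the intervention and how to capture those. Usual-care costs are not named. That is correct, so the protocol breaks no explicit promise. But the same objective is about the feasibility of an economic evaluation, and Phase 1 is meant to pilot the tools. The need for usual-care costs is an inference from these two statements, and a short one.

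**Visits are counted in everyone, so usual-care costs can be imputed.** In the second row of the table under reading A, 9 units over 9 attendances gives 1 per attendance. Four usual-care visits then cost 4, and 9 − 4 = 5 is the true difference. This stands if cost per attendance is the same in both phases and it is known which attendances the women counted. It remains an imputation: it does not test the question in usual care, and it carries no observed variation in spending among Phase 1 women.

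**The questionnaire is not shown and may be broader.** Section 7 describes a questionnaire that covers experience of either form of care. If it already asks all women about all expenses, only Section 8.5 needs to be brought into line.

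**A stronger reading is tempting.** A reader might infer that control women would count as zero and that the added cost to women would be overstated. The documents do not support this. Nothing tells an analyst to enter zero, and an expense that was not asked about is missing. No incremental cost is planned, and Step 4 shows that the direction is undetermined.

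**Conclusion.** The gap is real but limited to what the study pilots. Followed as written, Section 8.5 yields no expense data from the control cohort, about 20 women or half of those recruited. The expense question then goes untested in usual care, and there is no comparator or variance for women's costs to carry into the design of a later evaluation. Use of care is recorded in both phases, without a cost to the woman.

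No planned estimate is biased, and neither a direction nor a size of error in a cost difference can be given. The conclusion rests on two assumptions: that the questionnaire follows the scope in Section 8.5, and that Phase 1 women stay on existing care as Section 5.4.1 states. The change is worth making because it is cheap and the lost data cannot be recovered afterwards.

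**What to change.** In Section 8.5, and in the women's questionnaire if it has the same scope, ask every woman in both phases about all her out-of-pocket expenses for antenatal care: travel, fees and scans. In Phase 2, add a separate sub-item for the additional specialist classes, so that spending specific to the new service can still be identified. State that completeness, mean and SD will be reported descriptively for each cohort, with no test.

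The cost is the rewording of one item in a survey that both cohorts are already due to complete, and slightly more respondent burden in Phase 1.
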